## 1 DEFINITIONS AND ABBREVIATIONS

Term	Description
ABG	Air Bone Gap
CBAS	Cochlear Bone Anchored Solutions AB
CHL	Conductive Hearing Loss
COM	Chronic Otitis Media
COMOT	Chronic Otitis Media Outcome Test
CRF	Case Report Form
CRO	Contract Research Organisation
CSOM	Chronic Suppurative Otitis Media
DCF	Data Clarification Form
EC	Ethics Committee
eCRF	Electronic Case Report Form
EDC	Electronic Data Capture
ENT	Ear, nose and throat
GCP	Good Clinical Practices
GNP	Gross National Product
HL	Hearing Level
HRQoL	Health-Related Quality of Life
HUI	Health Utilities Index
ICD-10	International Statistical Classification of Diseases and Related Health Problems – Tenth Revision
ICF	Informed Consent Form
MERI	Middle Ear Risk Index
MHL	Mixed Hearing Loss
OM	Otitis Media
PI	Principal Investigator
PORP	Partial Ossicular Replacement Prosthesis
QoL	Quality of Life
SAP	Statistical Analysis Plan
SSQ	Speech, Spatial and Qualities of Hearing Scale
TORP	Total Ossicular Replacement Prosthesis

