### 4 BACKGROUND INFORMATION AND RATIONALE

#### 4.1 Introduction

Otitis media (OM) is an umbrella term used to describe inflammatory diseases of the middle ear, including acute OM, which may develop into chronic OM (COM) (1). COM subtypes are categorized as H65-H67 under International Statistical Classification of Diseases and Related Health Problems – Tenth Revision (ICD-10). COM is associated with the development of cholesteatomas (2), which are benign slow-growing tumours that develop in the middle ear space. Middle ear cholesteatomas are categorized under ICD-10 code H71 and are linked to poor patient outcomes since they can erode the middle ear space and middle ear ossicles (3). Global prevalence data show that 65–330 million individuals suffer from COM and that 60% of these individuals have significant hearing impairment (4). COM is characterized by recurring inflammation of the middle ear and mastoid cavity and may clinically present as otorrhea due to tympanic perforation in cases of chronic suppurative otitis media (CSOM) (5). The disease is normally triggered by an acute infection of the middle ear during

childhood (6). The World Health Organization defines OM to be chronic following two weeks of otitis media, whereas other clinical guidelines generally consider that acute OM be classified as COM when patients with tympanic perforations continue to discharge mucoid material for a time period of greater than six weeks to three months, despite medical intervention (7). Recurrent COM can occur due to a combination of several factors and is a significant health burden that affects patient quality of life (QoL) (8). COM is one of the most prevalent global chronic infectious diseases and may lead to hearing impairment (9), including both conductive hearing loss (CHL) and mixed hearing loss (MHL). One of the major causes of COM-associated hearing loss is ossicular discontinuity (10). Hearing losses may range from 20 to 60 dB hearing level (HL) and may be irreversible (11, 12). In children, the resulting hearing loss can negatively impact their speech development, their ability to learn and their behaviour (13, 14). COM in adults has been linked to significantly lower levels of QoL and is associated with anxiety and depression (15). Furthermore, if unsuccessfully treated, several life-threatening complications may arise, including brain abscesses and meningitis (16).

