### 7.2.1 Inclusion Criteria

Subjects must meet all of the inclusion criteria described below to be eligible for this clinical investigation.

1. Adult subjects, 18 years or older.
2. Subjects with conductive or mixed hearing loss.
3. Subjects with historically documented diagnosis of Chronic Otitis Media (COM) with or without cholesteatoma in the operated ear.
4. Subjects who have undergone primary tympanoplasty type I-V to improve hearing between 2010-2016.
5. Subjects with a PTA4 air-bone gap  $\geq 30$  dB OR PTA4 air-bone gap between 25-30 dB with an air conduction threshold PTA4  $\geq 40$  dB HL within 12 months after primary tympanoplasty in the operated ear.
6. Subjects who have been recommended by their health care professional to try a hearing aid to improve hearing in the operated ear.
7. Pre-op audiogram, maximum 1 year prior to the primary tympanoplasty, and post-op audiogram for the primary tympanoplasty are available.
8. Aided audiogram, unaided if no hearing device is used, available between 2018 and the point of enrolment.
9. Subjects are fluent in the language used for study questionnaires: German, French, Spanish.
10. Subjects are willing and able to provide written informed consent.
11. Medical Record data is available throughout the defined data search period, from primary tympanoplasty to point of enrolment.

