### 7.3.2.2 Study data from medical records

The medical record search for data extraction can start in parallel to the questionnaires/survey being answered.

Data to be collected from the medical records include:

- Demographics and hearing/device history information
- Pre- and post-primary tympanoplasty air and bone conduction audiograms (unaided and when applicable aided and PTA4 at minimum)
- Latest available (as per inclusion criteria) air and bone conduction audiograms (unaided and when applicable aided and PTA4 at minimum)
- COM-related contacts with health care providers for the operated ear (including name and number of interventions and/or procedures, medications and therapies, examinations and Middle Ear Risk Index factors and surgical outcomes where applicable)

More details on the information to be collected can be found in **Appendix 1**.

It might be the case in a few sites, that the required audiograms for some subjects were collected in a hearing aid partner centre/shop and not in the clinic itself. For these situations, clinics will reach out to the responsible audiologist and request a copy of the test.

For analysis, health care contacts, interventions and/or procedures will be coded using the ICD-10 coding system. Medication will be coded according to WHO CC ATC.

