## 9.2 Endpoints

### 9.2.1 Primary Endpoint

1. Categorical data collected from primary tympanoplasty to time of enrolment:
  - Number and type of contacts with health care providers
  - Number and type of interventions and/or procedures (medical examinations, surgical procedures, hearing rehabilitation)
  - Number and type of medications and therapies

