## 9.6 Primary Endpoint Analyses

COM-related health care utilisation, collected from medical records, from date of primary tympanoplasty to point of enrolment (analysed in patient-years) and CSRI questionnaire referring to the six-months prior to completion will be cross-checked to ensure data accuracy. Any overlapping extracts will be analysed as a single extract. Data from medical records related to information on health care contacts and costs for each contact (detailed variables are presented below) will be used in the analysis. Care consumption in the form of contacts, diagnoses and costs will be analysed with a view to identifying cost factors. All comparisons will be presented as aggregated data without the possibility of identifying data for individual subjects. Data coding will permit care episodes (a series of care contacts of the same individual) to be identified so that health care consumption and costs can be calculated per individual subject.

Health care utilisation will be mapped per individual subject and sub-analysis will be performed based on intervention subtypes, if feasible.

Health care contacts, interventions and/or procedures will be coded by ICD-10 classification. Medications will be summarised by higher level anatomical therapeutic classification (ATC) group and generic term. Therapies will be listed but not coded.

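### The stated coding rule for interventions and procedures uses a disease classification (ICD-10), which does not give the type of intervention that the primary endpoint reports

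*Combined protocol and SAP*

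**What the plan says.** The second component of the primary endpoint in 9.2.1 is "Number and type of interventions and/or procedures (medical examinations, surgical procedures, hearing rehabilitation"). It therefore has three broad classes, and the analysis must place each event in one of them.

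The coding rule appears twice. Section 7.3.2.2 says: "For analysis, health care contacts, interventions and/or procedures will be coded using the ICD-10 coding system". Section 9.6 repeats it: "Health care contacts, interventions and/or procedures will be coded by ICD-10 classification". Medications have their own scheme (ATC), and 9.6 says that therapies are listed without coding. Interventions and procedures are given no scheme other than ICD-10. Section 9.6 adds that "sub-analysis will be performed based on intervention subtypes, if feasible", but does not define the subtypes.

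Section 1 expands ICD-10 as "International Statistical Classification of Diseases and Related Health Problems", tenth revision.

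**The concern.** The rule codes one thing and the endpoint reports another. A disease code answers why the patient was seen; the endpoint asks what was done. An analyst who follows 9.6 literally would tabulate diagnoses where the endpoint calls for examinations, operations and rehabilitation.

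The study is descriptive and has no hypotheses, so the categories are the result. If they are not fixed in advance, someone will choose them after seeing the data, possibly in different ways for Germany, France and Spain. Section 9.4 also justifies the sample size by the ability to capture every intervention in standard care, and it singles out bone conduction solutions. That purpose depends on being able to identify intervention type.

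**Working it through.** The plan gives no figure on this point, so the check is mainly a comparison of its sections.

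**1. What the code supplies.** Section 4.1 uses ICD-10 for diagnoses: "COM subtypes are categorized as H65-H67 under International Statistical Classification of Diseases" and "Middle ear cholesteatomas are categorized under ICD-10 code H71". Section 9.7 (Survey - CSRI) uses it for medical history. In each place it describes a health condition. The documents name no ICD-10 code or national extension that describes a procedure.

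**2. How far it can separate events here.** Every subject must have a "historically documented diagnosis of Chronic Otitis Media (COM) with or without cholesteatoma in the operated ear". Appendix 1 limits contacts and examinations to COM-related ones for that ear. Three different events in the same ear, one from each endpoint class, could therefore share a diagnosis code. This is an illustration only: other ICD-10 codes may be used, and the documents contain no coding list from which to count how many events would collide.

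**3. Which component is affected.** Medications and therapies have workable rules. Contacts have their own *Type of contact* field in Appendix 1. The mismatch lies in interventions and procedures.

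**4. Whether the type is collected.** It is. Section 7.3.2.2 has sites extract the name and number of interventions and procedures, and Appendix 1 adds these fields:

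| Endpoint class | Fields in Appendix 1 |
|---|---|
| Medical examinations | *Exam or Procedure*, *Code of action/procedure* |
| Surgical procedures | Surgical Procedure section (only if available); *Type of contact* and *DRG Code* for the contact |
| Hearing rehabilitation | *Device type*, *Device name*; hearing aid history |

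No section says that these fields define type in the analysis, and no code system is named behind *Code of action/procedure*.

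**5. Costing.** Section 9.7 (Health care costs) applies standard unit costs in each country to the utilisation outcomes and assigns costs to individual contacts. Contacts carry type, DRG code, care provider and inpatient days. The section does not make the ICD-10 code the costing key.

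**6. Sample size.** The probability of seeing an intervention at least once is 1 − (1 − p)^n, with n = 200.
- At p = 0.02: 1 − 0.98^200 = 0.982, with 200 × 0.02 = 4 subjects expected. This reproduces the Table 1 cell and the stated 98%.
- At the quoted rate of 2.63%: 1 − 0.9737^200 = 0.995, with 200 × 0.0263 = 5.26 expected.

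The formula contains only n and p. The coding scheme does not enter it.

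**The case against.** The strongest reply is that the protocol already records type and that the coding sentence is only an addition. The name of each intervention is extracted, and Appendix 1 is laid out largely along the endpoint's three classes, so much of the classification follows from where an event is entered. Therapies show that the plan accepts reporting by name without a code. The subtype analysis is conditional on feasibility.

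Most of this stands, and it limits the point. A reader might infer that intervention type is not captured, or that the primary endpoint cannot be reported. The documents do not support that, because the fields exist and most carry no availability limit. A reader might also infer that the cost analysis fails because a diagnosis does not identify the unit to be costed. That would follow only if costs were keyed to the ICD-10 code, and 9.7 does not say so. Nor does it measure any effect to observe that none of the disease categories named in 4.1 identifies a procedure; that only restates what a disease classification is.

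The reply does not remove the mismatch. Two sections state a positive rule that interventions and procedures are coded by ICD-10 for analysis. No section says that type comes from the other fields, and neither section leaves the coding to another document. If a procedure classification was meant by ICD-10, the text does not name it.

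**Conclusion.** The point holds as a mismatch between a stated analysis rule and the primary endpoint, confined to the interventions and procedures component. It should be corrected before analysis. It is not a threat to the data, the sample size or, on the present text, the costing. Its numerical effect on the results cannot be derived from the documents.

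The conclusion assumes that ICD-10 means what Section 1 says it means. If the sponsor intended a procedure classification under that name, what remains is to name it and map it to the endpoint's classes.

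**What to change.** In 7.3.2.2 and 9.6, restrict ICD-10 to the diagnosis or the reason for the contact or procedure. Then add wording such as:

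*For the primary endpoint, interventions and procedures will be classified as medical examinations, surgical procedures or hearing rehabilitation, with bone conduction solutions shown separately. Classification will use the recorded intervention name, Exam or Procedure, Code of action/procedure, Type of contact, DRG Code, Device type (with Device name where needed) and, where available, the Surgical Procedure fields. Events that cannot be classified will be counted as type not specified.*

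Name the procedure code system behind *Code of action/procedure* in Germany, France and Spain, or the procedure classification that ICD-10 was meant to cover. Map it to these categories before analysis.

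The cost is two short text changes and one mapping table across three countries' code systems. The table is the real work. No new data and no change to N are needed. Because the surgical detail is collected only if available, some operations may be known by class but not by subtype, and the report should show how many events are left as type not specified.

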## 9.7 Secondary Endpoint Analyses

### Hearing performance

Audiogram data (see 9.2.2) collected pre- and post- primary tympanoplasty and between 2018 and point of enrolment will be compared to investigate how the standard of care impacts the subjects' hearing, when feasible. Wilcoxon signed rank test will be used to compare the audiometric test results.

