## 25 CHANGE HISTORY

Version	Change	Rationale
1.0	Initial version of document	NA
2.0	

Exclusion criteria on subjects with other chronic diseases removed.

French specific items removed and added to a country-specific CIP.

More details added on the number of subjects to be recruited and distribution per clinic.

More clarification on the sample size calculation.

More details added to the exploratory endpoints and its analysis.

Corrected order of exploratory objectives in section §6.3 to reflect ordering used in rest of document.

Added Investigator at Stage 2 in section §3

	Changes done in reply to comments from French Ethics Committee.

Version	Change	Rationale
3.0	
 
• Estimated recruitment period updated to reflect current plan.
 
• Clarification added if any site has difficulties with recruitment, the remaining sites are allowed to include more subjects than the even distribution initially planned, upon agreement with Sponsor.
 
• Upper limit of participating investigational sites increased from 6 to 9.
 
• Changes to the inclusion criteria: 
 
- Time window of primary tympanoplasty changed from 2015 to 2016.
 
- Hearing loss inclusion criteria on PTA4 air-bone gap <math>\geq 30</math> dB extended to cover patients with a PTA4 air-bone gap between 25-30 dB together with an air conduction threshold PTA4 <math>\geq 40</math> dB HL".
 
- Time window for post-op audiogram in hearing loss inclusion criteria extended to 12 months.
 
- Hearing aid inclusion criteria changed from have "tried a hearing aid" to have "been recommended by their health care professional to try a hearing aid".
 
 
 
• Monitoring services outsourced to Clinical Research Organisation (CRO) extended to French sites.
 
	
Changes done to reflect impact of COVID and administrative delays on the timeline and also to support recruitment efforts by increasing the pool of eligible subjects that represent the current standard of care in the participating countries and by allowing other sites to recruit more subjects if a specific one is having difficulties doing so.
 
CRO monitoring services extended to French sites due to changes of internal resources.

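### Because criterion 5 selects ears with a large residual air-bone gap, the signed-rank comparisons in section 9.7 cannot be read as the effect of standard of care on hearing

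*Combined protocol and SAP*

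**What the plan says.** Section 9.7 (Hearing performance) takes audiograms from three time points: before the primary tympanoplasty, after it, and between 2018 and enrolment. These "will be compared to investigate how the standard of care impacts the" hearing of the subjects, and "Wilcoxon signed rank test will be used to compare the audiometric test results". No test level is given, and nothing is said about how the ears were selected.

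Selection is set in section 7.2.1. Criterion 5 requires a PTA4 air-bone gap of at least 30 dB, or of 25-30 dB with air conduction PTA4 of at least 40 dB HL, "within 12 months after primary tympanoplasty in the operated ear". Criterion 7 reads: "Pre-op audiogram, maximum 1 year prior to the primary tympanoplasty, and post-op audiogram for the primary tympanoplasty are available". It sets no window for the post-operative audiogram and does not tie it to criterion 5. Appendix 1 lists one pre-operative, one post-operative and one latest audiogram for the operated ear. The change history (version 3.0) describes the criterion 5 measurement in the same terms: "Time window for post-op audiogram in hearing loss inclusion criteria extended to 12 months".

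On test conditions, section 9.2.2 collects unaided and, where applicable, aided thresholds. Criterion 8 asks for "Aided audiogram, unaided if no hearing device is used, available between 2018 and the point of enrolment".

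**The concern.** Criterion 5 acts on the middle one of the three measurements. An ear can meet it for two reasons: its true gap after surgery is large, or measurement error on that day made the gap look large. Each reason distorts a different contrast.

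**(a) Regression to the mean.** If the analysed post-operative audiogram is the qualifying one, its error is selected. With no true change, post-to-latest air conduction (AC) tends to look improved and pre-to-post AC tends to look worse.

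**(b) Selection on surgical outcome.** Whichever post-operative audiogram is analysed, the cohort is enriched for ears in which surgery did poorly. Pre-to-post and pre-to-latest contrasts therefore shift towards worsening.

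Without a caveat, an AC gain after the post-operative audiogram could be credited to later care, or could hide a small decline. A loss from the pre-operative audiogram could be blamed on standard of care when it partly describes who was enrolled.

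A separate, simpler point is that 9.7 does not say which conditions are paired. Criterion 8 accepts an aided latest audiogram, and every subject has been "recommended by their health care professional to try a hearing aid to improve hearing in the operated ear" (criterion 6).

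**Working it through.** The plan gives no power or precision figure for the audiometric contrasts, so there is none to reproduce. Negative shifts mean lower (better) thresholds.

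**Inputs from the protocol.** Criterion 5 cut-offs (7.2.1); 200 subjects (9.4); 30.0% of patients with a post-operative gap of at least 20 dB (4.2.2).

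**Assumed, because the protocol gives no values.** True post-operative gap normal with SD s = 8, 12 or 15 dB and mean m = 20 - 0.524s, so that 30% reach 20 dB; bone conduction (BC) mean/SD 15/8, 20/10 or 25/12 dB; AC = BC + gap; measurement error SD 1, 2 or 3 dB on each PTA4; two-sided 5% level. Ranges below are the minimum and maximum over the nine combinations of s and BC distribution.

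**Effect (a): direction.** The observed gap carries error e_AC - e_BC. Its covariance with e_AC is

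σ_AC² - ρ·σ_AC·σ_BC.

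This is positive for independent errors. It is zero when BC error is twice AC error and ρ = 0.5 (σ² - 0.5·2σ² = 0), and negative at ρ = 0.7 (σ² - 1.4σ² = -0.4σ²). The direction is therefore a tendency and not a certainty.

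**Effect (a): hand check.** Take a single cut-off at 30 dB, s = 12 and independent errors of 3 dB. Then m = 20 - 0.524×12 = 13.7, and the SD of the observed gap is √(144 + 9 + 9) = 12.73. The standardised cut-off is (30 - 13.7)/12.73 = 1.28, where the normal density divided by the upper tail is 0.176/0.100 = 1.75. The selected mean AC error is 9/12.73 × 1.75 = 1.24 dB. The full rule also admits ears at 25-30 dB, which lowers this somewhat.

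**Effect (a): simulation.** Post-to-latest AC, full criterion 5, no true mean change, 200 pairs:

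| Setting | Error SD 1 dB | 2 dB | 3 dB |
|---|---|---|---|
| Independent errors: shift (dB) | -0.1 to -0.2 | -0.4 to -0.8 | -0.8 to -1.7 |
| Independent errors: rejection | 14-59% | 46-97% | 78-100% |
| Plus individual later change, SD 5 dB: rejection | 5-10% | 14-48% | 40-96% |
| AC-BC error correlation 0.5: rejection | 6-27% | 17-72% | 30-95% |
| AC-BC error correlation 0.8: rejection | 5-14% | 7-32% | 13-60% |

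If BC error is twice AC error with correlation 0.5-0.7, the shift is -0.1 to +0.1 dB and rejection 4-15%. If the analysed post-operative audiogram played no part in selection, the shift is zero and rejection is about 5%. With no surgical change, pre-to-post is the mirror image of post-to-latest.

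**Effect (b).** Write true post-operative gap = true pre-operative gap + surgical change, where the change has population mean zero and SD c (assumed) and s stays the total SD. BC is 20/10 here. Selection sees the change only through the post-operative state, so

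E(change | selected) = (c²/s²) × (mean true gap in selected ears - m).

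For c = 5 dB, with the mean true gap in selected ears taken from the simulation:

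- s = 8, error SD 1: m = 15.8, selected mean 29.1; 25/64 × 13.3 = 5.2 dB.
- s = 15, error SD 3: m = 12.1, selected mean 32.9; 25/225 × 20.8 = 2.3 dB.

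Pre-to-latest AC therefore worsens by 2.3 to 5.2 dB, and the signed-rank test rejects in essentially every sample of 200 pairs. With c = 3 dB the worsening is 0.8 to 1.9 dB, and the test rejects in about two-thirds of samples or more. Only with c = 0, so that surgery changes no ear, is pre-to-latest rejection near 5% (4-6%).

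**Both together.** If the qualifying audiogram is analysed, the effects add in pre-to-post. For s = 8 and error SD 1 dB, this is 5.2 + 0.2 = 5.4 dB of apparent worsening.

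**The case against.** The strongest reply is that little hangs on this test. The endpoint is secondary, section 9.1 calls the analysis descriptive, section 9.3 states no hypotheses, no decision rule uses the p-value, and the comparison is made only when feasible. The objective in section 6.2 is neutral (to characterise long-term hearing), and section 7.1.1 already describes a population with residual hearing loss. That limits the severity. It does not remove the problem, because 9.7 still names a test and an impact reading without a caveat.

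A second reply is that the size of (a) rests on error SDs and correlations the protocol does not give. That stands: across the settings above, rejection runs from about 5% to 100%, and in one error structure the shift vanishes.

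Three stronger readings are tempting and are not supported:

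- *That the plan analyses the qualifying audiogram.* No section says so. Criterion 7, Appendix 1 and the change-history wording make it the natural reading, but effect (a) remains conditional on it.
- *That testing pre-operative against latest PTA4 avoids the problem.* Criterion 5 does not use the pre-operative audiogram, but it does select on the change that followed. Effect (b) in this contrast can exceed the artefact in (a).
- *That the worsening in (b) is spurious.* It is real in the enrolled ears. What fails is its attribution to standard of care.

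Nor does 9.7 say that aided and unaided thresholds will be mixed. Sections 7.3.2.2 and 9.2.2 list unaided plus, where applicable, aided data, which points towards unaided pairs. The pairing is simply unstated.

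**Conclusion.** The concern holds. Selection under criterion 5 means the comparisons in 9.7 describe the course of hearing in ears with a poor post-operative gap; they do not estimate what standard of care does to hearing.

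Effect (a) is conditional on the qualifying audiogram being analysed. It is small in dB (about 0.1 to 1.7 for independent errors of SD 1 to 3 dB, less with correlated errors, possibly nil), yet often enough to make a test on 200 pairs significant. Effect (b) does not depend on which audiogram is analysed. It is about 2.3 to 5.2 dB if individual surgical change has SD 5 dB and population mean zero. All SDs and correlations are assumptions; only the cut-offs, the 200 subjects and the 30.0% anchor come from the protocol. Severity is minor to moderate, and the primary endpoint is untouched.

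**What to change.** Change the wording of section 9.7 only:

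1. State which post-operative audiogram is analysed, and whether it is the criterion 5 audiogram.
2. Report all three contrasts descriptively (median or mean change with 95% CI, AC and BC separately), without p-values. Do not keep the pre-operative versus latest test as an unbiased alternative.
3. Add: *Subjects were selected for a residual air-bone gap on a post-operative audiogram (criterion 5). Changes to and from that audiogram are subject to regression to the mean, and changes from the pre-operative audiogram reflect selection for poor surgical outcome; neither estimates the effect of standard of care.* This sentence should accompany the intervals, since a CI that excludes zero invites the same misreading as a p-value.
4. Replace the aim with: *to describe the course of hearing in subjects selected for residual air-bone gap after tympanoplasty.*
5. Pair unaided with unaided thresholds and report aided thresholds separately.

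No new data are needed. The costs are the p-values and some pairs: device users without an unaided latest audiogram leave the unaided contrast. Their share is not given. If it were 20%, 40% or 60% of 200, then 160, 120 or 80 pairs would remain. Assuming error SD 3 dB and individual change SD 5 dB, the 95% CI half-width for mean AC change is 1.96 × √(2×3² + 5²)/√n, which grows from 0.9 dB at n = 200 to 1.0, 1.2 or 1.4 dB.
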